### 1.2.3. Removal of Subjects from Treatment

The participation of a subject in the study or the administration of treatment may be terminated at any time for one of the following reasons:

- The subject desires to discontinue study treatment.
- The subject withdraws consent to participate in the study.
- The subject is unwilling or unable to comply with the safety procedures.
- The subject is discovered to be pregnant.
- The subject experiences a medical emergency that necessitates withdrawal.

- The subject is withdrawn at the discretion of the Investigator for medical reasons or non-compliance.

#### 1.2.4. Stopping Rules

A subject should be removed from favipiravir treatment if one of the following criteria is met:

- Alanine transaminase (ALT) or aspartate transaminase (AST)  $> 8 \times$  upper limit of normal (ULN)
- ALT or AST  $> 3 \times$  ULN AND total bilirubin  $> 2 \times$  ULN
- ALT or AST  $> 3 \times$  ULN AND subject has right upper quadrant pain or eosinophilia
- Uric acid  $> 20$  mg/dL

A subject whose treatment is terminated should remain in the study for appropriate follow-up assessments.

#### 1.2.5. Study Procedures

The schedule of assessments, as outlined in the study protocol, is provided in [Table 1-1](#).

**Table 1-1 Schedule of Assessments**

| ASSESSMENT  | HOSPITALIZED      |                    |                |                 |                 |                 |                | FOLLOW-UP
Outsubject or Hospitalized |                    |   |
|---|-------------------|--------------------|----------------|-----------------|-----------------|-----------------|----------------|---|--------------------|---|
|   | DAY 1
PRE-DOSE | DAY 1
POST-DOSE | DAY 2          | DAY 3           | DAY 8           | Day 11          | DAY 14         | DAY 15 +
(-1 to + up
to 2 days    | DAY 29 ±
2 days | DAY 45
and 60 ± 2
days  |
| Informed Consent  | X                 |                    |                |                 |                 |                 |                |   |                    |   |
| Medical/Surgical
History                                     | X                 |                    |                |                 |                 |                 |                |   |                    |   |
| Physical Exam                                      | X                 |                    |                |                 |                 |                 |                |   |                    |   |
| Limited Physical
Exam                            |                   | X                  | X              | X               | X               | X               | X              | X                                       | X                  | X   |
| Concomitant
Medications Review                  | X                 |                    | X              | X               | X               | X               | X              | X                                       | X                  | X   |
| Review of Entry
Criteria                                     | X                 |                    |                |                 |                 |                 |                |   |                    |   |
| Vital Signs (BP, HR,
Temp, Resp)                 | X                 | X                  | X              | X               | X               | X               | X              | X                                       | X                  | X   |
| Clinical Laboratory
Exams                    | X                 |                    |                | X               | X               | X               |                | X                                       | X                  |   |
| Blood for antibodies to
SARS-CoV-2                           | X                 |                    |                |                 |                 |                 |                | X                                       | X                  |   |
| Blood for PK Sampling   | X     | X      | X  | X   | X   | X   | X  |   |                    |   |
| SpO 2 by Finger Sensor                   | X                 | X                  | X              | X               | X               | X               | X              | X                                       | X                  | X   |
| Urine or Blood
Pregnancy Test                                | X                 |                    |                |                 |                 |                 |                |   |                    |   |
| Nasopharyngeal and
Oropharyngeal Swabs
for Viral RNA, PCR | X                 |                    |                | X  | X  | X  |                | X                                       | X                  |   |

| ASSESSMENT   | HOSPITALIZED      |   |       |       |       |        |        | FOLLOW-UP
Outsubject or Hospitalized |                    |   |  |
|--|-------------------|---|-------|-------|-------|--------|--------|---|--------------------|---|--|
|  | DAY 1
PRE-DOSE | DAY 1
POST-DOSE  | DAY 2 | DAY 3 | DAY 8 | Day 11 | DAY 14 | DAY 15 +
(-1 to + up
to 2 days    | DAY 29 ±
2 days | DAY 45
and 60 ± 2
days  |  |
| and TCID 50   |                   |   |       |       |       |        |        |   |                    |   |  |
| Clinical Status – 6-
point Ordinal Scale              | X                 |   | X     | X     | X     | X      |        | X                                       | X                  | X   |  |
| National Early Warning
Score (NEWS2)                  | X                 |   | X     | X     | X     | X      |        | X                                       | X                  | X   |  |
| ECOG Performance
Status                               | X                 |   | X     | X     | X     | X      | X      | X                                       | X                  | X   |  |
| Study Specific
Symptom Status                         | X                 |   | X     | X     | X     | X      | X      | X                                       | X                  | X   |  |
| Randomization  | X                 |   |       |       |       |        |        |   |                    |   |  |
| Investigational Product
Dosing                                    |                   | Favipiravir Dosing Days 1-14
(1800mg BID on Day 1000mg BID Days 2-14)  |       |       |       |        |        |   |                    |   |  |
| Solicitation of
Treatment-Emergent
Adverse Events  |                   | X   | X     | X     | X     | X      | X      | X                                       | X                  | X   |  |
| Release from the Study   |                   |   |       |       |       |        |        |   |                    | X   |  |

1. Hematology, Chemistry (See Protocol Section 8.4).
2. May use results of labs taken at the hospital as part of SOC if done no more than 24 hours prior.
3. To be measured every day while hospitalized and at each clinic visit after hospital discharge through Day 60
  - a. Vital signs
  - b. Clinical Status 6-point scale
  - c. NEWS2
  - d. ECOG Performance status
  - e. Study-specific symptom status
  - f. Adverse Events
  - g. SpO2
  - h. Limited PE (heart and lungs)
4. PK on Day 1 prior to favipiravir dosing and between 45 to 75 minutes post-first dose.

5. PK trough samples to be taken approximately 30 minutes prior to any dose.
6. PK peak samples to be taken between 45 and 75 minutes post-dose.
7. Maintenance dose for CP score A is 800mg BID.
8. Days 45 and 60 may be completed in the hospital, outsubject clinic or by phone.
9. Subjects will undergo 9 planned venipunctures.
10. To be completed by PI or designee.
11. Days 3, 8, 11 Nasopharyngeal and Oropharyngeal Swabs for Viral RNA, PCR, and TCID50 may be done +/- 1 day from their scheduled day. Swabs will also be obtained on day of discharge from hospital if discharge occurs before Day 15.
12. To be checked throughout hospitalization and at clinic visits and changes only recorded as applicable.

## 1.2.6. Efficacy, Pharmacokinetic, and Safety Parameters

### 1.2.6.1. Efficacy Parameters

Efficacy will be measured through the following parameters:

For Primary Endpoint:

- PCR in the nasopharyngeal and oropharyngeal samples taken on Days 1, 3, 8, 11, 15 and 29. Swabs will also be obtained on day of discharge from hospital if discharge occurs before Day 15.

For Secondary Endpoint:

- Clinical improvement of hospitalized subjects with COVID-19 receiving either favipiravir + SOC or SOC alone as defined by the following study-specific 6-point ordinal scale assessed daily while hospitalized and at each outpatient visit until Day 60..
  1. Not hospitalized
  2. Hospitalized, not requiring supplemental oxygen
  3. Hospitalized, requiring supplemental oxygen
  4. Hospitalized, on non-invasive ventilation or high flow oxygen devices
  5. Hospitalized, on invasive mechanical ventilation or ECMO
  6. Death
- NEWS2 assessed daily while hospitalized and at each outpatient visit until Day 60.
- Vital signs (BP, HR, RR, BT, SpO2) measured daily while hospitalized and at each outpatient visit until Day 60.
- Patient status assessed daily while hospitalized and at each outpatient visit until Day 60 via Study-specific Symptom Status and ECOG Performance Status questionnaires
- Period of each respiratory assistance (if applicable).
- Period of hospitalization.
- Period of intensive care unit (if applicable).
- Date and cause of death (if applicable).
- TCID50 in nasopharyngeal and oropharyngeal swabs on Days 1, 3, 8, 11, 15 and 29. Swabs will also be obtained on day of discharge from hospital if discharge occurs before Day 15.

Note: Since TCID50 for SARS-CoV-2 is not yet proven to be sensitive for detection of the virus and is still under development for that purpose, analyses using TCID50 will not be conducted if TCID50 for SARS-CoV-2 is not detectable enough.
- Blood for determination of antibodies to SARS-CoV-2 obtained on Days 1, 15 and 29.

### 1.2.6.2. Pharmacokinetic Parameters

The PK measurement in blood samples taken on Days 1, 2, 3, 8, 11 and 14.

### 1.2.6.3. Safety Parameters

Abnormal clinical laboratory values that are clinically significant and all reported adverse events (AEs) will be graded according to the Common Terminology Criteria for Adverse Events (CTCAE) version 5.0.

Safety will be assessed by the following:

- Observed and reported AEs (including solicited and unsolicited events)
- Hematology and chemistry laboratories on Days 1, 3, 5, 8, 11, 15 and 29; if coagulation laboratory assays are ordered as part of the SOC, the results will be recorded
- Limited physical examination assessed daily while hospitalized and at each outpatient visit until Day 60.

## **2. SUBJECT POPULATION**

### **2.1. Population Definitions**

The following subject populations will be evaluated and used for presentation and analysis of the data:

- Intent-to-treat (ITT) population – All subjects randomized to treatment. Subjects in the ITT population will be analyzed based on the treatment to which they were randomized, irrespective of what treatment they actually received. This population was selected for the analysis of the primary and secondary endpoints in order to maintain the benefits of randomization and avoid the potential bias associated with the non-random loss of the participant.
- Safety population – All ITT subjects who received either favipiravir + SOC or SOC alone. Subjects in the safety population will be analyzed based on the actual treatment they received, irrespective of the treatment to which they were randomized. It is anticipated that the safety population will be the same as the ITT population.
- Modified intent-to-treat (mITT) – All subjects of the ITT population that have a post-baseline assessment of viral shedding and at least one PCR positive result for SARS-CoV-2 in any protocol-required swab samples. Note that results recorded as less than the lower limit of quantification (LLOQ) are considered to be negative. Subjects in the mITT population will be analyzed based on the treatment to which they were randomized, irrespective of what treatment they actually received.
- Per protocol (PP) population – All mITT subjects who adhere to relevant study procedures (i.e. have no major protocol deviation that would be expected to affect efficacy assessments) and have an outcome assessment.
- PK population (PK) – All subjects in the safety population that have at least one result that can be used in the PK summaries.

The ITT population is the primary population for the analysis of efficacy parameters; the mITT and PP populations will be used for supportive inferences concerning efficacy. The PK population is the primary population for the analysis of PK parameters. The Safety population is the primary population for the analysis of safety endpoints.

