9.4 Analysis Populations

The following analysis populations will be defined for the study:

• Intent-to-treat (ITT) population – All subjects randomized to treatment. Subjects in the ITT population will be analyzed based on the treatment to which they were randomized, irrespective of what treatment they actually received. This population was selected for the analysis of the primary and secondary endpoints in order to maintain the benefits of

randomization and avoid the potential bias associated with the non-random loss of the participant.

- Safety population All ITT subjects who received either favipiravir + SOC, or SOC alone. Subjects in the safety population will be analyzed based on the actual treatment they received, irrespective of the treatment to which they were randomized. It is anticipated that the safety population will be the same as the ITT population.
- Modified intent-to-treat (MITT) All subjects of the safety population that have an assessment of viral shedding after randomization and are confirmed COVID-19 positive. Subjects in the MITT population will be analyzed based on the treatment to which they were randomized, irrespective of what treatment they actually received.
- Per protocol (PP) population All MITT subjects who adhere to relevant study procedures and have an outcome assessment. Further specific details defining the analyses to be performed on this population will be described in the SAP.
- PK population (PK) All subjects in the safety population that have at least one result that can be used in the PK summaries.

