### **4.3. Efficacy Evaluation**

#### **4.3.1. Analysis of the Primary Efficacy Endpoint**

The primary endpoint of time to viral clearance will be analyzed with the log-rank test for treatment difference based on a two-sided alpha-level of 0.10 and summarized using Kaplan-Meier methodology. The time to viral clearance (in days) is defined as the time of Negative or Lower Limit of Quantification (LLOQ) results (without any quantitative results after that) as measured by PCR for SARS-CoV-2 via scheduled nasopharyngeal and oropharyngeal swab samples minus the date of first dose + 1.

Subjects who have no evidence of viral clearance will be censored at the time of the last PCR measurement with the following conditions:

- Patients whose symptoms worsen (defined as an increase of  $\geq 1$  point on the 6-point Ordinal Scale from baseline) on the day of the last PCR measurement, or who die will be censored at Day 29,
- Patients who are lost to follow-up will be censored on the day of the last PCR measurement.

The median time to viral clearance will be estimated based on the Kaplan-Meier estimator; additional summary statistics will be presented, including the 25th and 75th percentiles, 90% CIs (the log-log transformation) on the median and other percentiles and proportion of censored subjects. Viral clearance rates at Days 3, 8, 11, 15, and 29 will also be presented.

The analysis of the primary efficacy endpoint will be done using the ITT population.

The primary analysis will be supplemented with a sensitivity analysis, using a stratified log-rank test, where the treatment difference based on a two-sided alpha-level of 0.10 will be summarized and stratified by disease severity.

The analysis will also be repeated by the dexamethasone usage subgroup, where patients will be categorized as having received dexamethasone if they received it at any time prior to the last viral clearance assessment.

Kaplan-Meier curves will be provided for the overall ITT population. By-subject data listings of viral clearance data will also be provided.

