#### 4.3.2.8. Time to SARS-CoV-2 TCID50 Negative

Time to SARS-CoV-2 TCID50 negative in upper respiratory tract will be analyzed in a similar fashion as the primary efficacy endpoint. Time to SARS-CoV-2 TCID50 negative is defined as the time (in days) from initiation of study treatment (favipiravir + SOC or SOC alone) until a negative assessment in upper respiratory tract specimen.

Time to SARS-CoV-2 TCID50 negative will be performed on the mITT population.

Note: Since TCID50 for SARS-CoV-2 is not yet proven to be sensitive for detection of the virus and is still under development for that purpose, analyses using TCID50 will not be conducted if TCID50 for SARS-CoV-2 is not detectable enough.

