#### 4.3.2.9. Change in SARS-CoV-2 Viral Load

The change in SARS-CoV-2 viral load in upper respiratory tract specimen as assessed by area under viral load curve (quantitative PCR) as assessed up to 29 days. The area under the curve (AUC) over time for a given subject will be calculated, using the linear trapezoidal rule, as the sum of the maximum viral load for each day up through Day 29. Lower Limit of Quantification (LLOQ) result is considered as negative. An analysis of treatment group differences will be performed on the change in viral load using ANOVA model, with treatment group and disease severity as fixed factors.

The change in SARS-CoV-2 viral load will be analyzed by comparing the change between treatment groups using a mixed model with repeated measures (MMRM). This analysis will assess whether or not there is a difference in estimated change from baseline values between active treatment and SOC by visit using least squares means estimates from the MMRM. SAS PROC MIXED will be used to fit an MMRM with change from baseline in SARS-CoV-2 viral load as the response variable and the following covariates and fixed effects:

- Baseline SARS-CoV-2 viral load (covariate)
- Treatment group (fixed effect)
- Visit (fixed effect, time will be defined in terms of Visits)
- Time by Treatment Interaction (Time\*Treatment)

The covariance structure for the repeated measures in this model will be unstructured (UN). If UN does not converge for the model, a first-order autoregressive (AR(1)) covariance structure will be used.

Changes in viral load will be analyzed using the mITT population.

By-subject data listings will also be provided.

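### The mITT set admits subjects on a positive swab taken after treatment starts, so the viral-load and TCID50 analyses that rest on it are open to treatment-dependent selection

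*SAP*

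**What the plan says.** **Entry to mITT.** SAP 2.1 takes ITT subjects who have a post-baseline assessment of viral shedding and "at least one PCR positive result for SARS-CoV-2 in any protocol-required swab samples". It adds: "Note that results recorded as less than the lower limit of quantification (LLOQ) are considered to be negative".

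**Which swabs count.** SAP 1.2.6.1 lists "PCR in the nasopharyngeal and oropharyngeal samples taken on Days 1, 3, 8, 11, 15 and 29", plus a swab on the day of discharge if that comes before Day 15. Protocol 7.1 puts the Day 1 swab before dosing, and lists it ahead of randomization. Every other swab follows the start of treatment.

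**Where mITT is used.** SAP 4.3.2.9, which covers the AUC ANOVA and the change-from-baseline MMRM, states "Changes in viral load will be analyzed using the mITT population". SAP 4.3.2.8 states "Time to SARS-CoV-2 TCID50 negative will be performed on the mITT population". Neither section plans an ITT version. For the primary endpoint, SAP 4.3.1 states "The analysis of the primary efficacy endpoint will be done using the ITT population". SAP 2.1 says ITT was chosen for primary and secondary endpoints and that "the mITT and PP populations will be used for supportive inferences concerning efficacy".

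**The protocol's definition.** Protocol 9.4 takes safety-population subjects who "have an assessment of viral shedding after randomization and are confirmed COVID-19 positive". SAP Section 5 lists one change from the protocol, the removal of hierarchical testing. The new mITT definition is not listed.

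**The concern.** A subject who is positive on Day 1 meets the positivity condition whatever the treatment does. A subject who is negative, below LLOQ or without a result on Day 1 meets it only through a quantifiable swab after treatment has begun. If favipiravir lowers the chance of such a swab, fewer of these subjects enter from the favipiravir arm, and the two mITT arms are no longer the groups that randomization formed.

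Such subjects are foreseeable. Protocol inclusion criterion 1 allows the latest positive PCR to be up to 72 hours old, the first positive up to 7 days old, and symptoms to have begun up to 10 days earlier. The Day 1 study swab is a separate sample. After discharge, swabs are taken only when the subject can return, so early discharge also reduces the chances to qualify.

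The protocol's wording does not select in this way, because criterion 1 already requires a positive PCR. At stake are secondary virology results in a trial whose stated purpose is to show antiviral activity. The per-protocol set is drawn from mITT, so it offers no independent check.

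**Working it through.** **The plan's own figure.** The plan gives no number for this point. The only planning figure used below is 25 subjects per arm (protocol 9.2, SAP 3.1), and it reproduces. With exponential clearance and medians of 4 and 11 days, the rate ratio is 11/4 = 2.75. The chance of clearance by Day 15 is 1 - 2^(-15/4) = 0.926 and 1 - 2^(-15/11) = 0.611, mean 0.769. Freedman's formula at two-sided alpha 0.10 and 90% power gives 39.3 events and 39.3/0.769, about 51 subjects (52 in equal arms). The exponential rate-difference formula with pooled variance gives 25.3 per arm. The point does not depend on this.

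**Membership.** Let q be the share negative or below LLOQ on Day 1, and r the chance that such a subject has at least one later quantifiable swab. The documents give neither.

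- Expected mITT size per arm under the SAP rule: 25 × (1 - q + q × r).
- Expected difference, SOC minus favipiravir: 25 × q × (r_SOC - r_fav).
- Under a Day 1-only rule: 25 × (1 - q) in both arms, difference 0.

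With q from 5% to 30% and r pairs (SOC v favipiravir) of 0.5 v 0.25, 0.5 v 0.1 and 0.3 v 0.1, the difference runs from 25 × 0.05 × 0.2 = 0.25 to 25 × 0.30 × 0.4 = 3 subjects.

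**Unadjusted mean change.** All values here are assumed. Mean change is -2 log10 if positive on Day 1, the same in both arms; +2 if negative then positive; 0 if never positive. Later positivity is 40% on SOC and 20% on favipiravir.

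| | SOC | Favipiravir | Favipiravir minus SOC |
|---|---|---|---|
| q = 20%, mITT | (-40 + 4)/22 = -1.64 | (-40 + 2)/21 = -1.81 | -0.17 |
| q = 20%, all randomized | -36/25 = -1.44 | -38/25 = -1.52 | -0.08 |
| q = 10%, mITT | (-45 + 2)/23.5 = -1.830 | (-45 + 1)/23 = -1.913 | -0.083 |
| q = 10%, all randomized | -43/25 = -1.72 | -44/25 = -1.76 | -0.04 |

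The all-randomized contrast is the effect built into the assumptions. Selection adds the excess: 0.173 - 0.08 = 0.09 at q = 20%, and 0.083 - 0.04 = 0.04 at q = 10%.

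**Other inputs.** Take changes of -3 and +1 log10. At q = 10% and r = 0.5 v 0.25 the contrasts are -0.10 in mITT and -0.025 in all randomized, an excess of about 0.08. At q = 30% and r = 0.5 v 0.1 they are -0.54 and -0.12, an excess of 0.42. The result follows the assumptions closely.

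**AUC.** This measure sums viral load; it is not a change from baseline. Assume 100 units if positive on Day 1, 20 if only later positive and 0 if never positive, with q = 20% and later positivity as in the table.

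- mITT: SOC (2000 + 40)/22 = 92.7; favipiravir (2000 + 20)/21 = 96.2. Favipiravir looks 3.5 units worse.
- All randomized: SOC 2040/25 = 81.6; favipiravir 2020/25 = 80.8. Favipiravir is 0.8 units better.

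Dropping never-positive subjects removes low values mainly from the favipiravir arm, so here the direction reverses.

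**The case against.** The strongest reply is that the reach is small. The primary analysis is ITT, and SAP 4.3.1 sets out no mITT run of it; only the general line in SAP 2.1 points to supportive use. SAP 3.2 makes all non-primary p-values descriptive, no decision rule depends on mITT, and the TCID50 analysis may be dropped if the assay is not sensitive enough. Entry requires a recent positive PCR and Day 1 takes both nasopharyngeal and oropharyngeal swabs, so the Day 1-negative share may be low. All of this stands, and it confines the point to secondary analyses of uncertain exposure. It does not make the entry rule sound, since no other set is planned for viral load.

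Two stronger readings are tempting, and the documents support neither.

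- A reader might infer that the rule systematically favours favipiravir. The AUC illustration runs the other way, so no single direction can be claimed.
- A reader might take the whole 0.17 log10 in the illustration as bias. Of this, 0.08 is the assumed treatment effect on later positivity, which is present in all randomized subjects; selection adds only about 0.09.

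The figures are also raw means of one change per subject. The planned MMRM works by visit and adjusts for baseline viral load, which may reduce the excess; by how much is not quantified here.

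**Conclusion.** The concern holds for the analyses that use mITT: viral-load AUC, the viral-load MMRM and time to TCID50 negative. For subjects not positive on Day 1, entry depends on a result that treatment may change, and the departure from the protocol's definition is not declared.

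The size cannot be fixed from the documents, which give neither the Day 1-negative share nor later positivity rates. In the main illustration (10% to 20% below LLOQ on Day 1, 40% v 20% later positivity, +2 v -2 log10), selection adds about 0.04 to 0.09 log10 in favour of favipiravir to the unadjusted mean change. More extreme inputs give more. For AUC it can work against favipiravir. It would be wrong to infer that the primary result is affected: the primary analysis uses ITT and does not depend on this rule.

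**What to change.** 1. In SAP 2.1, replace the any-swab condition with a quantifiable PCR (at or above LLOQ) in the Day 1 pre-dose, pre-randomization nasopharyngeal or oropharyngeal swab, by the same rule in both arms. Name that swab explicitly. The SAP 3.5 baseline will not do, because for SOC subjects it may be a measurement taken after randomization.
2. In SAP 4.3.2.9, add an ITT sensitivity analysis of viral load. Requiring a post-baseline result is itself a post-randomization condition, and the new definition does not remove it.
3. In SAP Section 5, list the departure from the protocol's MITT definition.

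The cost is about one sentence in each place and one extra analysis, with no new data, visits or subjects. The downside is that the few Day 1-negative, later-positive subjects leave mITT; they stay in ITT.
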